120 stay. Endpoint 6 (readmissions) will be evaluated up to 12 weeks after hospital discharge.

121 1. Proportion of BG readings between 70 mg/dl and 180 mg/dl before meals

122 2. Number of hypoglycemia (< 70 mg/dl and 54 mg/dl) and severe hypoglycemia (< 40 mg/dl)
123 episodes during the first 10 days of therapy in the inpatient setting.

- 124 3. Number of episodes of severe hyperglycemia (BG > 240 mg/dl) after the first day of treatment
125 until the tenth day of therapy
- 126 4. Daily dose of basal insulin, daily dose of prandial insulin, and total daily dose
- 127 5. Length of hospital stay.
- 128 6. Number of readmissions (hospitalization) and Emergency room visits.
- 129 7. Cardiac complications are defined as myocardial infarction, cardiac arrhythmia requiring
130 medical treatment, or cardiac arrest.
- 131 8. Acute kidney injury defined as an increment in serum creatinine ≥ 0.3 mg/dL from baseline or
132 ≥ 1.5 times baseline creatinine (KDIGO) ²⁵.
- 133 9. Hospital mortality.

134

135 III.C Study type:

136 This is a prospective, randomized, open label multicenter trial to compare the safety and efficacy
137 of a basal bolus regimen with degludec and glargine in patients with T2D admitted to general
138 medicine and surgery services.

139

140 This study will include male or female subjects > 18 years. Due to the design of this hospital
141 study, there will be no run-in period. Upon arrival to the emergency department or medical or
142 general surgical wards, subjects will be screened. A total of 180 subjects will be analyzed. A
143 maximum of 108 (60%) surgical or medical patients will be randomized in the study to ensure a
144 balanced proportion of each group is included. Patients with a known history of T2D treated with
145 diet alone, any combination of OADs, short acting GLP-1 RA (liraglutide or exenatide) and
146 insulin prior to admission will be considered potential candidates for this study. Patients treated
147 with degludec, glargine U300 or with long-acting GLP1-RA (dulaglutide, albiglutide and weekly
148 exenatide) prior to admission will be excluded. Patients admitted with acute or chronic medical
149 illnesses, emergency or elective surgical procedures and trauma would be included in the study.

150

151 Insulin therapy will be aimed to maintain fasting and pre-meal blood glucose levels between 100
152 mg/dl and 180 mg/dL while avoiding hypoglycemia. Blood glucose levels between 70 and 100

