361 admitted to the hospital with an acute medical/surgical illness.

362 **Planned number of subjects to be randomized/started on study medication(s):** 180

363 **Anticipated number of trial sites:** 3 sites (Emory University Hospitals/Grady Hospital in
364 Atlanta, GA; additional Sites: Mount Sinai, NY-PI: [name] and Providence Medical
365 Research Centre PI: [name])

366 **Anticipated number of subjects to be randomised/started on trial medication(s) at each**
367 **trial site:** 60.

368 **Country planned to participate:** United States.

369

370 **Inclusion Criteria**

- 371 1. Males or females between > 18 years admitted to a general medicine or surgical service.
- 372 2. A known history of T2D treated either with oral monotherapy, any combination of oral
373 antidiabetic agents, short-acting GLP1-RA (exenatide, liraglutide) or insulin therapy
374 except for degludec and glargine U300.
- 375 3. Subjects with diet alone and HbA1c>7.0%
- 376 4. Medical and surgical patients expected to be admitted (LOS) longer than 2 days
- 377 5. Subjects must have a randomization BG > 140 mg and < 400 mg/dL without laboratory
378 evidence of diabetic ketoacidosis (bicarbonate < 18 mEq/L, pH < 7.30, or positive serum
379 or urinary ketones).
- 380 6. Signed, informed consent and HIPAA documentation prior to any study procedures

381

382 **Exclusion Criteria**

- 383 1. Subjects with increased BG concentration, but without a known history of diabetes (stress
384 hyperglycemia).
- 385 2. Subjects treated with diet alone (no antidiabetic agents) and admission HbA1c <7%.
- 386 3. Admission or pre-randomization BG≥400 mg/dl
- 387 4. Subjects with a history of diabetic ketoacidosis and hyperosmolar hyperglycemic state, or
388 ketonuria ³².
- 389 5. Patients treated with degludec or glargine U300, or with long-acting weekly GLP1-RA
390 (weekly exenatide, dulaglutide or albiglutide).
- 391 6. Patients with acute critical or surgical illness admitted to the ICU, except for observation
392 (<24 hours and did not require vasopressors and/or mechanical ventilation).
- 393 7. Patients with history of clinically relevant hepatic disease (diagnosed liver cirrhosis and
394 portal hypertension), ongoing corticosteroid therapy (equal to a prednisone dose ≥5
395 mg/day), or impaired renal function (eGFR< 30 ml/min), or congestive heart failure
396 (NYHA- IV).
- 397 8. Mental condition rendering the subject unable to understand the nature, scope, and

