398 possible consequences of the study.
- 399 9. Female subjects who are pregnant or breast-feeding at time of enrollment into the study.
- 400 10. Known or suspected allergy to trial medication(s), excipients, or related products.
- 401 11. Previous participation in this trial.

402

403 **Withdrawal Criteria**

- 404 1. The subject may withdraw at will at any time.
- 405 2. The subject may be withdrawn from the trial at the discretion of the investigator due to a
406 safety concern or if judged non-compliant with trial procedures or included in contravention
407 to the inclusion and/or exclusion criteria.

- 408 3. Subject admitted to the ICU who required continuous intravenous insulin infusion to maintain
409 glycemic control.
- 410 4. Pregnancy or intention to become pregnant.
- 411 5. Treatment with oral or injectable corticosteroid (equivalent or higher than prednisone
412 5mg/day), parenteral nutrition and immunosuppressive treatment after randomization.

413 **Treatment Failure Criteria**

414 Subjects with persistent hyperglycemia (≥ 2 glucose readings ≥ 400 mg/dL, ≥ 3 consecutive
415 glucose readings > 280 mg/dL, or with a mean daily blood glucose concentration ≥ 280 mg/dL)
416 and no treatable intercurrent cause for the hyperglycemia has been identified, will be considered
417 as treatment failure and discontinued from the study. Subjects will be started on continuous
418 insulin infusion if needed.

420 **Subject Replacement**

421 There will be no replacement of subjects in this trial.

423 **V. Visit Procedures**

424 Upon arrival to the emergency department or medical or general surgical wards, subjects will be
425 screened. Patients with a known history of T2D treated with diet alone, any combination of
426 OADs, and insulin prior to admission will be considered potential candidates for this study.
427 Patients admitted with acute or chronic medical illnesses, emergency or elective surgical
428 procedures and trauma would be included in the study.

429 Patients will be treated with a basal bolus insulin regimen as previously reported. In brief,
430 subjects treated with insulin prior to admission will receive 80% of the total daily outpatient
431 insulin dose given. Insulin naïve patients will discontinue oral agents and will receive a starting
432 total daily dose (TDD) of 0.4 U/kg/day for BG between 140 mg/dl and 400 mg/dL. The starting
433 TDD will be reduced to 0.3 U/kg/day in patients ≥ 70 years or with a GFR < 60 ml/min. Both

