488 juice/snack (crackers) as per protocol. If the patient is not awake: 50ml (1 amp) will be given
489 STAT. Blood glucose levels will be repeated in 15 minutes and dextrose administration will be
490 repeated as needed for values < 70 mg/dl.

491

492 **Subject Compliance**

493 Aim 1. Inpatient (hospital) trial. We will use electronic medical records and nursing records to
494 document day and time of insulin administration of study drug (degludec and glargine) given
495 once daily and prandial- rapid-acting insulin (aspart) given before meals. We will also record
496 dose and number of units given as supplement (correction) to correct hyperglycemia.

497

498 Aim 2. Patients will be contacted every 2 weeks after discharge by a study coordinator to assess
499 insulin administration, glycemic control, hypoglycemia and medication adherence. Patients are
500 to bring all used and unused insulin pens (study drug). Patients will keep daily record of time
501 and dose of insulin administered every day during the study period.

502

503 **VI. STATISTICAL CONSIDERATIONS:**

504 **VI.A Aim 1. To determine differences in inpatient glycemic control in patients treated with**
505 **degludec or glargine in patients with T2D.**

506 **Sample Size and Power Calculations:**

507 The primary endpoint in this study is glycemic control measured by mean daily BG
508 concentration. To show the non-inferiority of degludec and glargine in terms of glycemic
509 control, we set the equivalence margin as 18 mg/dl (1 mosm/l), from a view that a difference <18
510 mg/dl is usually not considered as clinically significant^{12-14,37}. Based on the results of the Rabbit
511 medicine and surgery trials, it is reasonable to assume the standard deviation of mean daily BG is
512 bounded above by 45 mg/dl. Assuming the true BG difference between the treatment groups is
513 zero, and using one-sided, two-sample t-tests, we require 78 subjects for each treatment group to
514 achieve 80% power with alpha=0.05. Accounting for 10-14% attrition rate, we would need 90
515 patients per treatment group, which means 180 subjects in total, to achieve >80% power in Aim
516 1.
517

518 **Analysis of Primary Endpoint:**

519 The primary endpoint for Aim 1 is non-inferiority in mean differences between treatment groups
520 in their mean blood glucose concentrations during the first 10 days of therapy (non-inferiority

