581 questions, and a member of the research staff will answer questions. The principal investigator
582 (PI) will also be available at all times to answer questions that participants may have during the
583 consent procedure or during the time a participant is enrolled in the study. The consent form will
584 be completed only by trained research personnel familiar with the study protocol procedures,
585 informed consent process, who have undergone CITI training in accordance with the IRB
586 guidelines of Emory University. A signed copy of the consent form will be provided to the
587 participant and a copy will be placed in the file that is maintained for each participant in the
588 study office.

589 The study will be conducted in accordance with the Declaration of Helsinki and will be
590 conducted in accordance with the ICH GCP guidelines. The sponsor-investigator will comply
591 with all applicable regulatory and legal requirements, ICH GCP guidelines and the Declaration
592 of Helsinki in obtaining and documenting the informed consent.

593
594 **Recruitment Procedure.**

595 We screen all patients with hyperglycemia admitted to the hospital every day. Patients with
596 diabetes and hyperglycemia will be identified electronically following inclusion/exclusion
597 criteria. Once a potential candidate is identified, we will approach the primary team as well as

598 the patient and family for consent. We estimate that we will screen approximately 220-250
599 patients to analyze a total of 180 subjects, and expect to recruit about 2-4 patients per week”

600
601

602 **IX. STUDY SCHEDULE:**

FIRST PATIENT IN	DEC 2017
SCREENING	~220-250
ANALYZED	180
LAST PATIENT RECRUITED	MARCH 2020
LAST PATIENT IN	JUNE 2020
DATA ANALYSIS	AIM 1: 09/2020 ; AIM: 2: 12/2020
SUBMISSION TO CONGRESS OR JOURNAL	1/ 2021 (ADA); 4/2021: EASD

603

604 **X. STUDY DRUGS AND MATERIALS:**

605 **Study medication(s) / devices(s)**

606 Degludec insulin (U-100): 100 units/mL (U-100): 10 mL multiple-dose vial (1 vial per subject
607 during hospital admission): Inpatient arm: 90 patients. Total number of vials: 90

608 Degludec insulin 100 Units/mL, provided in 3 mL pen cartridges (outpatient arm).

609 Outpatient arm: 90 patients, average insulin dose: 30-45 U/day. Total number of cartridges: 100

610

611 Glargine insulin (U-100): 100 units/mL (U-100): 10 mL multiple-dose vial (1 vial per subject
612 during hospital admission): Inpatient arm: 90 patients. Total number of vials: 90

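### 180 is given both as the number randomised and as the number analysed, although the sample-size section treats it as the number before 10-14% attrition

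*Combined protocol and SAP*

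**What the plan says.** **180 as the number analysed.** Section III.C states "A total of 180 subjects will be analyzed". Objective 1 in Section II gives the same figure. The Recruitment Procedure in Section VIII estimates that 220-250 will be screened and speaks of "patients to analyze a total of 180 subjects, and expect to recruit about 2-4 patients per week". The Study Schedule in Section IX has a row for subjects analysed, also set at 180.

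**180 as the number randomised.** Section III.C lists two groups of n=90. The Section IV entry "Planned number of subjects to be randomized/started on study medication(s") is 180, with 60 at each of three sites.

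**How 180 was obtained.** Section VI.A requires 78 per group for 80% power, allows for 10-14% attrition, and arrives at 90 "patients per treatment group, which means 180 subjects in total, to achieve >80% power in Aim" 1. Section VI.B repeats this for Aim 2 and describes 78 as the number left after attrition.

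**Rules that govern the analysed number.** The Subject Replacement paragraph says "There will be no replacement of subjects in this trial". Section III.B puts into the primary analysis every participant who received at least two doses of study drug.

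**The concern.** Section VI.A makes 180 a number before losses. If 180 are randomised, some are lost and none are replaced, then fewer than 180 are analysed. Yet four places in the protocol promise an analysed 180.

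Three things are at stake:

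- **When enrolment stops.** A reader of Section IV stops at 180 randomised. A reader of the schedule could go on until 180 are analysable.
- **How the completed trial will look.** If attrition falls where the plan expects, the report will seem to miss a pre-stated analysed number by 18 to 25 subjects, although the sample-size reasoning was met or very nearly met.
- **What power a reader infers.** Taking 180 as analysed suggests a larger reserve than Section VI.A built in.

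**Working it through.** **Inputs, all from Section VI.A unless noted**

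- Margin: "we set the equivalence margin as 18 mg/dl (1 mosm/l").
- SD of mean daily BG: "bounded above by 45 mg/dl", used here at 45.
- True difference: "Assuming the true BG difference between the treatment groups is" zero.
- Test: one-sided two-sample t-test, alpha 0.05, target power 80%.
- Attrition: 10-14%.
- Randomised: 90 per group, 180 in total (Sections III.C and IV).

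**Step 1: reproduce the plan's 78.**

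n per group = 2 × [SD × (z0.95 + z0.80) / margin]² = 2 × [45 × (1.645 + 0.842) / 18]² = 77.28, rounded up to 78. Exact noncentral-t power at 78 per group is 80.0%. The plan's figure is confirmed.

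**Step 2: reproduce the 90.**

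Randomised per group = 78 / (1 − attrition):

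- 10%: 78 / 0.90 = 86.7, so 87
- 13%: 78 / 0.87 = 89.7, so 90
- 14%: 78 / 0.86 = 90.7, so 91

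The stated 90 covers attrition up to 1 − 78/90 = 13.3% and is one subject per group short at 14%. That is rounding.

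**Step 3: apply the plan's attrition to 180 randomised, counting each loss as a loss from the analysis.**

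- 10%: 180 × 0.90 = 162 (81 per group), 18 fewer than 180
- 14%: 180 × 0.86 = 154.8, about 155 (77.4 per group), 25 fewer than 180

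**Step 4: power at each size (margin 18, SD 45, true difference 0, one-sided 0.05).**

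Normal approximation: power = Φ(18 / (45 × √(2/n)) − 1.645). Exact t: the same noncentrality, with 2n − 2 degrees of freedom.

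| Situation | n per group | Exact t | Normal |
|---|---|---|---|
| 14% attrition | 77.4 | 79.7% | 80.05% |
| Plan's requirement | 78 | 80.0% | 80.3% |
| 10% attrition | 81 | 81.3% | 81.6% |
| All 180 analysed | 90 | 84.8% | 85.0% |

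Reading 180 as analysed raises the apparent power by 84.8 − 81.3 = 3.5 points at 10% attrition and by 84.8 − 79.7 = 5.1 points at 14%.

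**Step 5: how much the 14% result depends on the SD.**

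The plan gives 45 as an upper bound. Exact-t power at 77.4 per group is 80.05% with SD 44.8, 81.3% with SD 44 and 87.3% with SD 40.

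**The case against.** The strongest reply is that the documents already show what 180 means. Section VI.A derives it from 78 evaluable per group. In Section III.C, the sentence after the quoted one limits medical or surgical patients randomised to 108, or 60%, and 60% of 180 is 108. A careful reader can work out that 180 is the enrolment target, and no test or margin depends on the word used. This is fair, and it is why the point is modest. It does not remove the conflict, because the analysed figure appears in four places, one of them the schedule.

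The second reply is that the two-dose rule weakens any firm analysed number. Basal insulin is given once daily and eligible patients are expected to stay more than 2 days, so a subject who leaves after the second dose still counts. This stands. A reader might infer that only 155-162 subjects can be analysed, or that 200-210 must be randomised to analyse 180 (180/0.90 = 200; 180/0.86 = 209.3, so 210). The documents support neither, since both assume that every attrition case leaves the analysis set, and attrition is never defined that way. The analysed number could lie between about 155 and nearly 180. Even so, if attrition does not mean loss from that set, Section VI.A had no reason to raise 78 to 90.

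**Conclusion.** Wrong as written, at a cost of wording only. The plan gives 180 as both randomised and analysed, while its own attrition allowance and its no-replacement rule imply about 155-162 evaluable. That range assumes that the 10-14% is loss from the two-dose analysis set.

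A reader might also conclude that the claim of more than 80% power fails at 14% attrition. The documents do not support that as a material finding. The gap is 0.3 percentage points by exact t and absent by the normal approximation. It amounts to less than one subject per group (77.4 against 78), and it needs the upper-bound SD and the upper-end attrition to occur together. The accurate description is about 80-81% over the stated attrition range, with no reserve at the upper end. The plan's 78 reproduces exactly, and its 90 reproduces to within one subject per group.

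**What to change.** 1. In Objective 1, Section III.C, the Recruitment Procedure and the Study Schedule row, replace the analysed 180 with: 180 randomised; at least 156 (78 per group) required in the primary analysis; about 155-162 expected if the 10-14% attrition is loss from the set with at least two doses.
2. In Section VI.A, define attrition against that analysis set, for example as randomised subjects who receive fewer than two doses or contribute no usable glucose data. The expected range in item 1 depends on this definition, so the two should be agreed together.
3. In Section VI.A, restate the claim of more than 80% power as about 80% at the upper end of the attrition range (SD 45). Carry the same wording into Section VI.B, which reuses the calculation.

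No change to the number randomised is needed. If the sponsor wants at least 80% power strictly at 14% attrition, 91 per group (182 in total) is enough. The cost is a text edit, and the stated figures become slightly less favourable.

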153 mg/dL are still considered at goal, however BG values in this range will trigger insulin
154 adjustment to minimize the risk of hypoglycemia as recommended by professional associations.
155 Patients with T2D will be randomized to receive:

156 **Group 1.** Basal bolus with degludec once daily and aspart insulin before meals (n=90)

157 **Group 2.** Basal bolus with glargine U100 once daily and aspart insulin before meals (n=90)

158

159 **Aim 1. Inpatient (Hospital) Arm:** Patients will be treated with a basal bolus insulin regimen as
160 previously reported.^{12-14,16} In brief, subjects treated with insulin prior to admission will receive
161 80% of the total daily outpatient insulin dose given. Insulin naïve patients will discontinue oral
162 agents and will receive a starting total daily dose (TDD) of 0.4 U/kg/day for BG between 140
163 mg/dl and 400 mg/dL. The starting TDD will be reduced to 0.3 U/kg/day in patients ≥ 70 years
164 or with a GFR < 60 ml/min. Both groups will be treated with bolus regimen given half of TDD
165 as basal (degludec or glargine) once daily and half as aspart divided in three equal doses before
166 meals. Patients with poor oral intake or with medical instruction to withhold oral intake (NPO)

167 will receive the basal dose, but prandial dose will be held.¹⁴ Insulin dose will be adjusted daily to
168 maintain a fasting and pre-dinner BG between 100 mg/dl and 180 mg/dl.

169

170 **Initiation and Dosing of Basal insulin**

171 Patients treated with insulin prior to admission will receive 80% of their total home daily insulin
172 dose. Half of the total daily dose will be given as basal degludec/glargine) and half as prandial
173 (aspart) insulin. The basal insulin will be given at the same time every day. The prandial
174 (aspart) insulin will be held in patients with poor oral intake or NPO, but they will receive the
175 usual basal insulin dose.

176 Insulin naïve patients will receive a starting insulin dose of 0.4 U/kg/day. Half of the total daily
177 dose will be given as basal degludec/glargine) and half as prandial (aspart) insulin. The basal
178 insulin will be given at the same time every day. The prandial (aspart) insulin will be held in
179 patients with poor oral intake or NPO, but they will receive the usual basal insulin dose.

180 **Adjustment/Titration of daily insulin dose:**

181 The basal insulin dose will be adjusted daily per fasting blood glucose concentration. The target

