182 BG concentration during insulin treatment is 100-180 mg/dl. The daily basal (degludec/glargine)
183 dose will be increased by 10% if the fasting BG is between 180 and 240 mg/dl or by 20% if
184 fasting BG concentration is >240 mg/dL. The total daily insulin dose (basal and prandial insulin)
185 will be increased by 20% in patients with mean BG > 240 mg/dl. In addition, the basal insulin
186 dose will be reduced by 10% if any BG is between 70-100 mg/dl, and by 20% in patients with
187 any BG < 70 mg/dl. The total daily dose will be reduced 30-40% in the event of severe
188 hypoglycemia (BG < 40 mg/dl).

189 Several clamp studies in patients with type 1 and type 2 diabetes and observations from clinical
190 practice showed that insulin degludec quickly reaches steady state after the 2nd or 3rd day of
191 therapy, a similar period reported with other basal insulin analogs^{26,27}. Based on its steady-state
192 condition, clinical pharmacology studies show that insulin degludec has a flatter, less variable
193 and more consistent glycemic effect.

194 **Treatment randomization.** Patients will be randomized using a computer-generated
195 randomization table. Treatment randomization/assignment will be coordinated by the research
196 pharmacy. A research pharmacist at each institution will follow a computer-generated block
197 randomization table based on glucose levels (BG≤200 or BG>200) at randomization.
198

199 **TREATMENT PROTOCOL - Basal Bolus Insulin Regimen with Degludec or Glargine** 200 **Once Daily plus Aspart before Meals**

201 **Patients Treated with Insulin Prior to Admission**

- 203 • Discontinue oral antidiabetic drugs on admission.

204 Subjects treated with insulin prior to admission will receive 80% or 100 % of the total daily
205 dose (TDD) given as basal bolus regimen.

206

207 **Starting Insulin Doses:**

- 208 - **BG < 200 mg/dl give 80% of TDD***
- 209 - **BG ≥ 200 mg/dl give 100% of TDD***

210

- 211
212 • Half of TDD will be given as degludec or glargine and half as rapid-acting insulin.
213 • Degludec and glargine will be given once daily at the same time of the day
214 • Patients will receive the full-dose of degludec or glargine (even if NPO) the day of
215 surgery or diagnostic procedure(s).
216 • Aspart insulin will be given in three equally divided doses before each meal. To prevent
217 hypoglycemia, if a subject is not able to eat, aspart insulin dose will be held.

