218 *** If patient was on basal only therapy consider adding prandial dose as calculated above.**
219

220 **Insulin Naïve Patients Treated with Oral Agents or GLP1-RAs**

- 221 • Discontinue oral antidiabetic drugs on admission.
222 • Starting total daily insulin dose:
223 ▪ 0.4 U/Kg/day when randomization BG between 140-400 mg/dL
224 ▪ Reduce TDD to 0.3 units per kg in patients ≥ 70 years of age and/or with an eGFR $<$
225 60 ml/min.
226 • Half of TDD will be given as glargine or degludec and half as aspart.
227 • Degludec or glargine will be given once daily, at the same time of the day.
228 • Patients will receive the full-dose of degludec or glargine insulin (even if NPO) the day
229 of surgery or diagnostic procedure(s).
230 • Aspart insulin will be given in three equally divided doses before meals. To prevent
231 hypoglycemia, if a subject is not able to eat, the dose of aspart insulin will be held.
232

233 **Supplemental insulin.** Aspart insulin will be administered following the “supplemental or
234 correction insulin scale” protocol (Appendix 1, page 21). Supplemental doses will be given for
235 BG > 140 mg/dl before meals. At bedtime, supplemental insulin will be reserved for patients
236 with BG > 250 mg/dl.

- 237 • If a patient is able and expected to eat most of his/her meals, supplemental insulin will be
238 administered before meals and at bedtime following the “usual” dose of the insulin scale
239 protocol.
240 • If a patient is not able to eat, supplemental insulin will be administered every 6 hours
241 (Appendix 1) following the “sensitive” dose of the supplemental insulin scale protocol.
242

243 **Basal Insulin adjustment.**

- 244 • Daily basal insulin dose will be adjusted as follow:
245 ▪ If the fasting and/or pre-dinner BG is between 100 - 140 mg/dl in the absence of
246 hypoglycemia the previous day: no change
247 ▪ If the fasting and/or pre-dinner BG is between 141 - 180 mg/dl in the absence of
248 hypoglycemia: increase basal insulin by 10% every day*
249 ▪ If the fasting and/or pre-dinner BG is 181 – 299 mg/dl in the absence of
250 hypoglycemia the previous day: increase basal insulin (degludec or glargine) dose by
251 20% every day*
252 ▪ If the fasting and/or pre-dinner BG is ≥ 300 mg/dl in the absence of hypoglycemia the
253 previous day: increase basal insulin (glargine) dose by 30% every day*
254 ▪ If the fasting and pre-dinner BG is between 70 - 99 mg/dl in the absence of

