455 chemistry)
456

457 **Assessments for Safety**

458

459 **Potential Risks to the Subject:**

460

461 **Protection against risks:**

462 We will follow safeguards to minimize the risk to our subjects: a) we will carefully monitor
463 capillary BG at the bedside using a hand-held glucose meter, b) only experienced nurses/or
464 phlebotomist will draw blood samples, and c) women of reproductive age who are sexually
465 active will undergo a urine pregnancy tests prior to participation in the study. To prevent
466 significant clinical events, no patients with history of significant liver (diagnosed liver cirrhosis
467 and portal hypertension), renal impairment (eGFR<30ml/min/1.73m²) or severe cardiac failure
468 will be recruited in this study.

469 **Hypoglycemia:** It is possible that following the proposed protocol, patients receiving
470 insulin degludec or glargine may develop hypoglycemia. The risk of hypoglycemia (BG < 70
471 mg/dl) in non-ICU patients treated with subcutaneous insulin is between 5–30%^{13,33-35}. The
472 number of hypoglycemia (< 70, < 54 and < 40 mg/dl) will be analyzed statistically. For the
473 purpose of this analysis, hypoglycemia is defined as follows: 1) BG < 70mg/dL is a glucose alert
474 value, 2) BG < 54 mg/dL will be considered as clinically important hypoglycemia, and 3) Severe
475 hypoglycemia, will be defined as a BG < 40 mg/dl.^{16,36} We expect that approximately 10% in the
476 inpatient setting and ~20% in the outpatient (post-discharge) arm will experience one or more
477 episodes of hypoglycemia. To minimize the risk of hypoglycemia, the starting dose will be
478 reduced in the basal bolus insulin regimen (TDD: 0.4 units per kg of body weight), in addition, in
479 patients ≥ 70 years of age and/or eGFR < 60 ml/min the TDD will be further reduce to 0.3
480 units/kg. To avoid hypoglycemia, the total daily dose of insulin will be decreased by 10% for
481 BG between 70-99 mg/dl and by 20% after each episode of hypoglycemia (BG < 70 mg/dl). In
482 addition, in patients treated with insulin at home, the TDD of insulin will be reduced by 20% on
483 admission and the attending physician may further reduce insulin dose in the presence of severe
484 hypoglycemia.

485
486 Hypoglycemia will be treated with dextrose infusion. Dextrose 50% solution will be given for
487 glucose values < 70 mg/dl. If the patient is awake, 25 ml (1/2 amp) will be given IV or oral

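### The inpatient insulin rules contradict one another on starting dose, up-titration and low readings, and nothing says which governs

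*Combined protocol and SAP*

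**What the plan says.** Section III.C contains two full sets of inpatient dosing rules. Section V repeats parts of them.

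- **Starting dose, patients already on insulin.** The Aim 1 overview gives 80% of the home dose with no BG condition, and Initiation and Dosing of Basal insulin says the same: "Patients treated with insulin prior to admission will receive 80% of their total home daily insulin" dose. Section V, Visit Procedures, agrees: "subjects treated with insulin prior to admission will receive 80% of the total daily outpatient" insulin dose. The TREATMENT PROTOCOL, under Starting Insulin Doses, gives 80% below 200 mg/dl but otherwise says "BG ≥ 200 mg/dl give 100% of TDD". The Hypoglycemia paragraph under Protection against risks lists as a safeguard that "addition, in patients treated with insulin at home, the TDD of insulin will be reduced by 20% on" admission, again with no BG condition.
- **Raising basal insulin.** Adjustment/Titration of daily insulin dose works from fasting BG: the basal "dose will be increased by 10% if the fasting BG is between 180 and 240 mg/dl or by 20% if" it exceeds 240. It adds a 20% rise in total daily dose (TDD) when mean BG is above 240. Basal Insulin adjustment, in the TREATMENT PROTOCOL, uses fasting and/or pre-dinner BG and starts lower. Its first step reads "If the fasting and/or pre-dinner BG is between 141 - 180 mg/dl in the absence of" hypoglycaemia and raises basal by 10%. It then gives +20% at 181–299 and +30% at 300 or more.
- **Low readings.** Adjustment/Titration cuts basal by 10% if any reading is 70–100. Basal Insulin adjustment cuts TDD by 10% when fasting and pre-dinner BG are 70–99. The Hypoglycemia paragraph cuts TDD by 10% for BG 70–99 without naming which reading counts.

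There are two smaller slips. The row for 300 mg/dl or more in Basal Insulin adjustment names only glargine. Section V gives the titration target as 80–180 mg/dl, where Section III.C gives 100–180.

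**The concern.** Insulin dosing is the intervention, and hypoglycaemia is its main stated risk. Staff cannot follow all of these rules at once, and the text does not tell them which to follow. The Hypoglycemia paragraph also promises an admission reduction that the TREATMENT PROTOCOL withholds from patients with BG of 200 or more.

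The trial is open label at three sites, and its outcomes are glucose, hypoglycaemia and insulin dose (secondary endpoint 4). If sites or clinicians follow different lists, dosing varies for reasons unrelated to treatment. There is then no single standard for judging a protocol deviation, or the incorrect-dose errors that Section XII asks investigators to record.

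**Working it through.** The plan gives no figure on this point to reproduce, and the Aim 1 sample size uses none of these rules. The check applies each written rule to the same patient. List A is Initiation and Dosing plus Adjustment/Titration. List B is the TREATMENT PROTOCOL, including Basal Insulin adjustment.

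**1. Starting dose, prior insulin, BG ≥ 200.** The ratio of B to A is 1.00 / 0.80 = 1.25. The documents give no home doses, so these are assumed:

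| Assumed home TDD (U/day) | A: 80% | B: 100% | Gap (U/day) |
|---|---|---|---|
| 40 | 32 | 40 | 8 |
| 60 | 48 | 60 | 12 |
| 80 | 64 | 80 | 16 |

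Half is given as basal, so at 60 U/day the basal start is 24 U under A and 30 U under B.

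**2. One-step basal change.** Fasting and pre-dinner BG are both at the value shown, mean BG is at most 240, and no reading is 100 or lower:

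| BG (mg/dl) | A | B | Ratio B/A |
|---|---|---|---|
| 160 | 0 | +10% | 1.10 / 1.00 = 1.10 |
| 200 | +10% | +20% | 1.20 / 1.10 = 1.09 |
| 260 | +20% | +20% | 1.00 |

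A value of 160 lies inside the 100–180 target. A leaves the dose alone, while B raises it daily.

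**3. Low readings, none below 70.**

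- *Fasting 85, pre-dinner 160.* A finds a reading in 70–100 and cuts basal by 10%. B's cut, read literally, needs fasting and pre-dinner BG both at 70–99, so it does not apply. The pre-dinner value of 160 triggers +10%. The Hypoglycemia paragraph cuts TDD by 10%.
- *Fasting 160, pre-lunch 85, pre-dinner 160, bedtime 150.* A cuts basal by 10%. B raises it by 10%, because it bars an increase only after hypoglycaemia, defined as below 70.

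In both cases the basal doses compare as 1.10 / 0.90 = 1.22. On an illustrative basal dose of 30 U that is 33 against 27 U after one step, a gap of 6 U or 20% of the current dose.

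**4. Gaps within a single list.** With fasting 120 and pre-dinner 200, the patient meets both the no-change and the +20% rows of B. With fasting 200 and pre-lunch 85, the patient meets both the +10% and the −10% rules of A. Neither list says which prevails.

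**5. Where the lists agree.** For BG below 70 both reduce insulin by 20%, A in basal and B in TDD. For BG below 40 both cut TDD by 30–40%.

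**The case against.** The best defence is that the TREATMENT PROTOCOL is the operative text and the rest is summary. Its heading and bulleted orders suggest so, and the Aim 1 overview and the Section V paragraph present themselves as short accounts of a previously reported regimen. That explains those two places. It does not explain Initiation and Dosing or Adjustment/Titration, which have their own headings, are written as orders and use different thresholds. Nor does it explain the safeguard in the Hypoglycemia paragraph.

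A second argument is that the low-reading conflict is a drafting slip. The other range rows in Basal Insulin adjustment say and/or, and Section III.C elsewhere says that readings of 70–100 should prompt an adjustment to limit hypoglycaemia. The intent probably is a cut. But reading the row as and/or puts the patient with fasting 85 and pre-dinner 160 in both the −10% and the +10% rows of one list. It does nothing for the pre-lunch reading of 85, which that row never considers.

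Other points stand and limit the finding:

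- Once triggered, the cuts agree on basal size, since a 10% cut in basal and prandial insulin includes a 10% basal cut. The differences are in the trigger and the prandial dose.
- The reversal needs a mixed profile, with one reading low and another at 141 or above.
- No effect on hypoglycaemia has been estimated, and every list cuts insulin below 70.
- The 100% start is the patient's own home dose.
- Randomization is blocked by BG ≤ 200 against > 200 at each institution. Apart from a value of exactly 200, this balances exposure to the starting-dose conflict between arms.

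**Conclusion.** The concern holds. The current text contains three conflicts and no order of precedence. The starting dose differs by 25% for prior-insulin patients with BG of 200 or more. One-step basal changes differ by 10 percentage points at BG 160 and at BG 200. For some mixed profiles the lists point in opposite directions, 20 percentage points apart.

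The percentages follow directly from the written rules. The unit figures rest on assumed home doses of 40–80 U/day and an illustrative 30 U basal dose. The documents do not say how many patients would be affected.

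This needs correcting because contradictory insulin orders are a safety problem and one stated safeguard is not delivered. The effect on the treatment comparison is mainly added variability, because both arms share the rules. Bias between arms is possible in an open-label trial but is not shown.

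**What to change.** Keep one governing inpatient dosing and titration table, and have every other place in Sections III.C and V refer to it. The choice of starting-dose and up-titration rules belongs to the sponsor's clinicians. The table should:

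1. give one starting dose for prior-insulin patients, with its BG condition if there is one;
2. give one set of increase thresholds and name the readings that count;
3. state that any reading of 70–99 or lower overrides any increase, and say whether the cut applies to basal or to TDD;
4. state which row applies when fasting and pre-dinner BG fall in different rows.

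Rewrite the admission-dose sentence in the Hypoglycemia paragraph to match the chosen starting dose. As minor corrections, name both basal insulins in the row for 300 mg/dl or more, and change the 80 mg/dl target floor in Section V to 100.

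The cost is a protocol amendment and a site memo. Sample size and analysis do not change.
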